6.6.1 Risks associated with arterial cannulation

Arterial cannulation will be performed by a trained physician according to standard hospital procedures (see Section 11.2.1). The risk of accidental extravascular infusion is assessed as minimal. Backflow of blood will be checked before infusion and saline will be infused to verify correct placement.

The subjects will be lying still in bed during the treatment with the arm in the same position and the risk of dislocation during the treatment period is considered minimal.

In case of accidental extravascular infusion, no local toxicity is anticipated due to the low concentrations infused (see Section 6.6.2). Also due to the continuous wash-out by the flowing blood in combination with the short half-life of C21, no accumulation of C21 to the tissue is expected.

In very rare instances, insertion of arterial catheters may cause blocking of the artery, tearing of the artery, arterial leakage, poor healing, or infection at the insertion site [13]. To mitigate such risks, the cannula used will be small, the puncture will be done with a stylet rather than by using a guidewire and a Seldinger technique. Further, the duration of the FBF assessment procedure is short, which limits the risk of infection.

After removal of the catheter a compression bandage will be applied to prevent bleeding. Written instructions regarding how to handle the bandage, how to manage symptoms and when to contact the Investigator will be provided to the subject before leaving the clinic.

6.6.2 Risks related to local tolerance

The risk for local tissue irritability by C21 in this model has been thoroughly assessed and it has been concluded that a dedicated nonclinical local tolerance study is deemed not to be needed. This reasoning is based on:

1. The general safety findings generated in nonclinical and clinical studies with C21 [8].

- 2. The daily doses to be used in this small exploratory study are between 100 to 300 times below the established safe oral human doses. Hence, the initial total dose given i.a. will be a microdose of 15 μ g C21 and the maximal dose will be 1 mg (total daily dose 1.715 mg). For comparison, the established safe single human therapeutic oral dose is 200 mg.
- 3. The highest concentration of C21 that will be infused into the arterial blood is 100 μ g/mL, and with an infusion rate of 2 mL/min, the temporary local intravascular concentration of C21 is estimated, including potential variance in the local blood flow, to be significantly below 10 μ g/mL, which can be compared to the mean systemic C_{max} of 230 μ g/mL achieved in monkeys without any safety concerns [8]. As a comparison, the systemic mean systemic C_{max} after a single oral 200 mg dose is approximately 4.5 μ g/mL.
- 4. The study design is following a careful dose escalation strategy, which allows timely risk mitigation to take place. Thus, any potential reactions at the infusion site will be closely monitored by the Investigator and any signs of tissue irritability or pain will be promptly detected (the subjects are awake) and the infusion can be discontinued if deemed necessary.

6.6.3 Risk assessment with regards to the COVID-19 pandemic

Current recommendations from the authorities will be considered on a day-to-day basis. Assessment sessions with Sponsors, Investigators, and contract research organisation (CRO)/vendor representative members to align on local restrictions, impact assessment, contingency plans and study-specific risk mitigation strategies will be made to safeguard the study conduct and the safety of the subjects included in the study. Risks regarding subject safety, study performance and data quality/integrity will hence be assessed on an ongoing basis during the study. The risks and mitigating actions will be documented in a risk log as part of the Sponsor's trial master file (TMF).

European Medicines Agency Guidance on the Management of Clinical Trials during the COVID-19 pandemic as well as local guidelines from the Swedish Medical Products Agency have been taken into consideration. Planned prevention and mitigating actions are outlined in Table 6.6-1. Risks and mitigating actions will be updated as applicable over the course of the study.

This study has a short in-person time frame including a healthy population. Hence, study participation is not expected to confer increased risks to the subjects in terms of COVID-19 exposure.

Table 6.6-1 COVID-19 related risks and mitigating action	VID-19 related risks and mitigating action	S
--	--	---

Risks identified	Actions
Subjects may be exposed to the severe acute respiratory syndrome coronavirus 2 (SARS-CoV-2), which may lead to subsequent development of COVID- 19.	In accordance with recommendations by the Public Health Agency of Sweden (Folkhälsomyndigheten), subjects are not allowed to visit the clinic if they have any symptoms that may be COVID-19-related, as assessed by the Investigator. Subjects will be reminded about the restrictions by a text message, that will be sent to the subjects prior to each visit. The absence of COVID-19-like symptoms will also be verified in association with site entry.
	COVID-19 Ag rapid tests (Humasis) for detection of the SARS- CoV-2 nucleocapsid and the SARS-CoV-2 spike receptor binding domain from nasal swabs might be performed in participating subjects when arriving to study visits. Testing will be used in the study as long as it is indicated due to the spread of SARS-CoV-2 in the community. The performance and the result of each test will be documented in the subject's medical records. If a subject tests positive, the subject will be sent home and the event will be reported as an AE. Rapid testing will be performed as needed based on the prevailing COVID-19 situation at the time of study conduct as judged by the Investigator. Rapid testing will not be performed at screening visits or at visits with a shorter duration, such as follow-up visits. Adjustments will be made at the research clinic so that an acceptable physical distance can be maintained between the subjects The subjects will be recommended not to use public transport to and from the clinic. Subjects will be supplied with hand disinfectants to be used during clinic visits. All door and drawer handle and basins at the sites will be disinfected
Callingto and a till	each day.
between visits and will therefore not be able to	AEs and compliance will be followed up by phone calls. Subjects with suspected Covid-19 symptoms will be asked to seek SARS- CoV-2 testing.
come to the clinic site for study assessments within allowed time windows.	Subjects who test positive for COVID-19 between visits will be referred to standard hospital care if needed.
Subjects may get ill with Covid-19-like symptoms during a visit.	There is a clear action plan if a subject becomes ill during the site visit. The subject will be isolated and unless unwarranted for safety reasons, the subject will be sent home, and carefully followed up with phone calls by site staff. If the subject cannot be sent home due to safety reasons, the subject will be isolated and site staff who are in contact with the subject have to wear protective clothing and equipment. The Principal Investigator or delegate will contact the nearest infection clinic and decide on further actions.
The hospital laboratory may not be able to analyse safety samples due to the number of COVID-19 samples.	An accredited lab has been contracted as a back-up lab for analysis of safety samples.

Risks identified	Actions
New recommended actions by health authorities, such as society lock-down if the pandemic escalates, which will cause a halt in the	This risk does not affect subject safety.
study.	
On-site monitoring is not possible to perform in accordance with the monitoring plan due to the Covid-19 outbreak and entry restrictions to the site.	Remote centralised monitoring activities will be increased as will centralised review of data.
Increased number of protocol deviations due to the Covid-19 outbreak.	All protocol deviations will be documented and handled according to the CTU's standard operating procedures (SOPs).

6.6.4 Risk-benefit conclusion

Overall, the combined safety data from the pre-clinical and clinical studies have not revealed any safety issues that would outweigh the expected value of the study. While keeping the above-mentioned risk factors at a minimum level to not expose the subjects participating in the study for risks that would not be ethically justifiable, it is concluded that the planned assessments are considered sufficient to meet the scientific purpose of the study and the potential benefits will outweigh the potential risks for the participating subjects.

More detailed information about the known and expected benefits and risks, and reasonably expected adverse reactions of C21 is found in the current version of the C21 IB [8].

7 STUDY OBJECTIVES AND ENDPOINTS

7.1 Primary objective

The primary objective is to investigate the effect of C21 on FBF measured by strain-gauge venous occlusion plethysmography in healthy male subjects.

7.1.1 Primary endpoint

The primary endpoint is percent change from baseline in FBF, in response to increasing i.a. doses of C21.

7.2 Secondary objectives

The secondary objectives are:

- To establish the dose-response curve for C21.
- To explore the method of measuring FBF by strain-gauge venous occlusion plethysmography by using sodium nitroprusside as a positive control.
- To evaluate safety and tolerability of i.a. administrations of C21 to healthy male subjects.

7.2.1 Secondary endpoints

The secondary endpoints are:

- Dose-response curve of C21.
- Percent change from baseline in FBF, in response to increasing i.a. doses of sodium nitroprusside.
- Frequency, intensity and seriousness of AEs.
- Clinically significant changes in vital signs, ECG and safety laboratory parameters.

8 STUDY DESIGN

8.1 Overall study design and schedule of events

This is a phase 1, open-label, single-centre study investigating the effects of i.a. infusions of the AT_2R agonist C21 on FBF in 5 healthy male subjects, by use of strain-gauge venous occlusion plethysmography.

Consenting subjects will be screened for eligibility according to study-specific eligibility criteria (see Sections 9.4 and 9.5) within 30 days prior to IMP administration (Visit 1; screening).

Eligible subjects will be scheduled for a treatment visit (Visit 2; Day 1). Relevant inclusion/exclusion criteria will be confirmed and a standardised meal (breakfast or lunch depending on the time of the day) will be served 60 minutes (min) prior to the first FBF measurement.

Measurements of FBF will be performed using a Conformité Européenne (CE)-marked automated strain-gauge venous occlusion plethysmography equipment providing on-line measurements, following a pre-specified procedure (see Section 11.2.1).

The subjects will be placed resting in a comfortable supine position in a quiet room with normal room temperature (+20 to +25° C) [14] with the forearms positioned above the level of the heart. Cuffs will be placed on the widest part of both forearms and a smaller cuff will be placed around each wrist. The non-infused arm is used as a contemporaneous control to account for any minor changes in FBF affecting both arms, *e.g.* emotional stress or temperature changes.

A catheter will be inserted into the brachial artery of the nondominant arm following standard hospital procedures (see Section 11.2.1) and a resting period of approximately 25 min will follow. At the end of this resting period, baseline measurements of FBF will be performed.

Ascending doses of C21 (3, 10, 30 100 and 200 μ g/min) will be administered through local i.a. infusions for 5 min/dose with an infusion rate of 1 mL/min or 2 mL/min for the 200 μ g/min dose. Measurements of FBF will be performed in both arms simultaneously during the last 2 min of each infusion/dose. The C21 doses will be separated by a wash-out period of at least 15 min. At the end of each wash-out period FBF will be measured and a baseline value for the next dose will be recorded. The Investigator will assess any emerging AEs by subject interview between each dose before deciding to proceed to the next dose level.

A flow-chart of the C21 dosing and FBF measurement schedule is presented in Figure 8.1-1.

Figure 8.1-1 Dosing and measurement flow-chart for C21 infusions

When the last C21 dose has been administered there will be a resting period of 20 min. At the end of this resting period, FBF will be measured and a baseline value for the first sodium nitroprusside dose will be recorded.

CONFIDENTIAL

Infusions of sodium nitroprusside solution (Nipruss[®]) will be performed as a positive control, using the same methodology as described above. Ascending doses of 0.8, 1.6, and 3.2 μ g/min will be administered. A flow-chart of the Nipruss[®] dosing and FBF measurement schedule is presented in Figure 8.1-2.

Safety assessments (blood pressure, pulse, ECG, and safety laboratory parameters) will be performed prior to first dose of IMP and before the subject leaves the clinic. Any occurrence of AEs during the procedure will be recorded.

After removal of the arterial catheter a compression bandage will be applied to prevent bleeding. Written instructions regarding how to handle the bandage, how to manage symptoms and when and how to contact the Investigator if necessary, will be provided to the subject before leaving the clinic.

A follow-up phone call (end-of-study) will be performed 7 to 10 days after the treatment visit (Visit 2).

The schedule of events is shown in Table 8.1-1. Study assessments are described in Section 11.

Table 8.1-1 Schedule of events

		Screening	Treatment	End-of- study
Visit/contact	Refer to CSP section:	Visit 1	Visit 2	Follow-up call
Assessment		Day -30 to Day -1	Day 1	Day 8 to Day 11
Informed consent	14.3	X		
Inclusion/exclusion criteria	9.4, 9.5	X	\mathbf{X}^{1}	
Demographics	11.1.3	X		
Weight, height, BMI	11.1.4	X		
Medical/surgical history	11.1.5	X		
HIV, hepatitis B and C	11.1.6	X		
Alcohol test	11.1.7	X	Х	
Urine drug screen	11.1.8	X	Х	
Physical examination	11.1.9	X		
Clinical laboratory profile ²	11.3.4	X	X ³	
Vital signs (blood pressure and pulse)	11.3.2	X	X^3	
12-lead safety ECG	11.3.3	X	X ³	
Standardised breakfast/lunch	9.6.1		X^4	
IMP administration	10.5		Х	
FBF measurements (plethysmography)	11.2.1		X^5	
Baseline symptoms	11.1.11	X	X ⁶	
Adverse events	11.3.1		X^7	X
Prior and concomitant medications	11.1.10	X	Х	X

1. Confirmation of relevant inclusion/exclusion criteria.

2. Clinical chemistry, haematology and coagulation.

3. Before first IMP administration and before leaving the clinic.

4. Served 60 min prior to first FBF measurement.

5. For detailed procedures and timepoints, see Section 11.2.1.

Until start of study procedure on Day 1.
 From start of study procedure on Day 1.

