9.9 Randomisation and blinding

Randomisation will not be used. This is an open-label study and all subjects will receive the same IMP and undergo the same study procedures.

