The subject will receive ascending doses of C21 (3, 10, 30, 100 and 200 μ g/min) through local i.a. infusions for 5 min/dose with an infusion rate of 1 mL/min or 2 mL/min for the 200 μ g/min dose. The start -and stop times of the infusions will be recorded. Measurements of FBF will be performed in both arms simultaneously during the last 2 min of each infusion. The C21 doses will be separated by a wash-out period of at least 15 min. At the end of each wash-out period FBF will be measured and a baseline value for the next dose be recorded.

For each FBF measurement, an inflation pressure of 60 mmHg will be used for intervals of approximately 7 sec followed by approximately 8 sec of deflation. This cycle will be repeated approximately 8 times during the last 2 min of each infusion. The wrist cuff will be inflated to supra-systolic pressures within 30 sec before each measurement to exclude the hand circulation. Changes in forearm volume will be measured using strain-gauges placed around the widest part of the forearms. A measure of blood flow to that part of the forearm enclosed by the two cuffs is provided, expressed as mL per 100 mL of forearm volume per minute. Actual forearm volume can be estimated by calculation, assuming the forearm is a simple truncated cone, or by simple water displacement.

When the last C21 dose has been administered, the infusion will be discontinued and there will be a resting period of 20 min. At the end of this resting period, FBF will be measured and a baseline value for the first sodium nitroprusside dose will be recorded.

Infusions of sodium nitroprusside solution (Nipruss[®]) will be performed as a positive control, using the same methodology as described above. Ascending doses of 0.8, 1.6, and 3.2 μ g/min will be administered.

After removal of the arterial catheter a compression bandage will be applied to prevent bleeding.

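### The dose-response model in 17.5.2 has neither a baseline nor a control-arm term, so session drift cannot be told apart from dose; the stated role of the non-infused arm is not carried into the analysis

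*Combined protocol and SAP*

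**What the plan says.** The synopsis, 8.1 and 11.2.1 all give the non-infused arm the same task: "The non-infused arm is used as a contemporaneous control to account for any minor changes in FBF affecting both arms". Emotional stress and temperature are the examples given. Data for it are collected: "Measurements of FBF will be performed in both arms simultaneously during the last 2 min of each infusion/dose".

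The endpoints do not mention it. Section 7.1.1 reads "The primary endpoint is percent change from baseline in FBF, in response to increasing i.a. doses of C21", and the matching secondary endpoint in 7.2.1 is "Percent change from baseline in FBF, in response to increasing i.a. doses of sodium nitroprusside". Neither names an arm, a ratio or a difference.

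Section 17.1 provides a separate FBF baseline for each dose level. Sections 17.5.1 and 17.5.3 summarise percent change from it descriptively, by dose. Section 17.5.2 takes another route: a mixed model for the natural log of the largest FBF value per subject and dose, with dose as a categorical effect and subject as random. It lists no baseline, time or control-arm term. Its outputs are a plot of the LSMeans and a table of their pairwise differences.

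On order, 9.9 states "Randomisation will not be used", and 11.2.1 gives every subject the same ascending sequence. Section 17 leaves technical detail to a separate SAP, to be signed before database lock. That SAP is not among the documents.

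**The concern.** The protocol describes a correction, but a reader cannot tell whether or how it will be made. This has two consequences, of different weight.

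- **Dose-response (17.5.2).** Dose rises with time in every subject. A gradual change in FBF over the session, in the absence of any drug effect, would have the form of a dose-response curve. That curve is a stated secondary endpoint, and 6.5 says that the data will guide further studies.
- **Percent-change summaries (17.5.1, 17.5.3).** Each dose is referred to its own baseline, so slow drift largely cancels. What remains is a change shared by both arms between a baseline and its own infusion. A shared rise would look like vasodilation and a shared fall would hide it. Only the non-infused arm can show this.

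**Working it through.** The plan gives no drift, SD, between-arm correlation, alpha or power, so there is no figure of its own to reproduce. Every size below is illustrative.

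**1. Aliasing.** For 5 subjects and 5 doses in one fixed order, the design matrix has rank 5 with dose alone, 5 with dose plus period and 5 with dose plus linear time. Time adds no rank, so infused-arm readings alone cannot separate it from dose.

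**2. Apparent effect of 200 versus 3 µg/min with no drug effect.** The first and fifth infusions start 4 × (5 + 15) = 80 min apart, taking the minimum wash-out.

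| Shared change, all 5 subjects | 17.5.2 as written | Own-dose baseline | Concurrent infused/non-infused ratio |
|---|---|---|---|
| +20% steady drift over 80 min | +20% | 0 | 0 |
| +10% between baseline and infusion, at 200 only | +10% | +10% | 0 |

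The first row reflects the absence of both a baseline and a control-arm term, since either one removes it. Only the second row isolates what the control arm alone can do.

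Expressed per dose step, shared drift of 2, 5 or 10% gives 1.02^4 − 1 = 8%, 1.05^4 − 1 = 22% or 1.10^4 − 1 = 46%. If only 3 or 1 of the 5 subjects drift by 20%, the bias is 1.2^(3/5) − 1 = 11.6% or 1.2^(1/5) − 1 = 3.7%. If the direction of drift varies at random between subjects (log SD 0.18), there is no bias, but the contrast SD rises from 0.059 to √(0.0591² + 0.1823²/5) = 0.10 (first variance setting in step 4).

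**3. Slow drift left in percent change.** The baseline precedes its infusion reading by about 5 min, so the residue is (1 + d)^(5/80) − 1. For d = 10, 20 or 30% this is 0.6, 1.1 or 1.7% at each dose.

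**4. Precision cost.** Assume 8 readings per arm at each measurement and a reading SD of 0.10 on the log scale, so a mean has reading variance 0.01/8 = 0.00125. Let s_common and s_arm be the shared and arm-specific SDs within subject. Using means throughout, the SD of a contrast between two doses is:

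- infused arm: √(2(s_common² + s_arm² + 0.00125)/5)
- concurrent log ratio: √(2(2 s_arm² + 0.0025)/5)

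| s_common / s_arm | Infused arm | Log ratio |
|---|---|---|
| 0.05 / 0.05 | 0.050 | 0.055 |
| 0.08 / 0.06 | 0.067 | 0.062 |
| 0.10 / 0.05 | 0.074 | 0.055 |
| 0.12 / 0.12 | 0.110 | 0.112 |

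The ratio is more precise only if 2 s_arm² + 0.0025 < s_common² + s_arm² + 0.00125, that is, s_arm² < s_common² − 0.00125.

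Own-baseline adjustment of the infused arm gives √(4(s_common² + s_arm² + 0.00125)/5), which is 0.071 at 0.05/0.05 if baseline and infusion deviations are uncorrelated. With correlation 0.8 between a baseline and its own infusion it is √(4(0.2 × 0.005 + 0.00125)/5) = 0.042, below the unadjusted 0.050. The cost therefore depends on a correlation that the documents do not give.

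**The case against.** **The SAP may settle it.** This stands in part. If the SAP defines the modelled FBF as control-corrected or baseline-corrected, the defect in 17.5.2 disappears. A reader might infer that the control arm will go unused, and the documents do not support that. However, Section 17 claims to give the principal features, and 17.5.2 is specific enough to name the dependent variable, both model terms and the degrees-of-freedom method.

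**Drift is hypothetical.** This stands as to size. The protocol expects minor changes only, and limits them with rest, a quiet room, a standardised meal, and caffeine, nicotine and exercise restrictions. Nor does 17.5.2 specify a significance test, so no false-positive rate should be attributed to it.

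**The primary endpoint is protected.** This stands for slow drift. A reader might infer that session drift biases the primary result, but the own-dose baseline leaves at most 1.7% in step 3.

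**The ratio looks more precise.** At 0.05/0.05 the planned log maximum has contrast SD √(2(0.0025 + 0.0025 + 0.00373)/5) = 0.059, against 0.055 for the mean log ratio. That comparison changes two things at once. Moving from maximum to mean takes 0.059 to 0.050, and bringing in the control arm then raises it to 0.055. No general gain in precision can be claimed, and maximum versus mean is a separate question.

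**Both arms may already be measured at baseline.** Probably so. The sentence "At the end of each wash-out period FBF will be measured and a baseline value for the next dose be recorded" does not say which arms, but the procedure also says "Changes in forearm volume will be measured using strain-gauges placed around the widest part of the forearms". One clarifying line is enough.

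**Conclusion.** The point holds as a low-cost improvement. As written, 17.5.2 cannot separate session drift from dose, because it omits both the recorded same-dose baseline and the concurrent control arm under one fixed ascending order. That follows from the design and needs no assumption about drift. Its size does: the contrast is biased by whatever shared drift occurs, such as +20% for an assumed 20% rise in all subjects.

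For the primary and nitroprusside summaries the gap is narrower. It concerns only a shared change between a baseline and its own infusion, which would pass through in full. The case for using the control arm is protection against that bias, and the precision figures rest on assumed variances.

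**What to change.** 1. **17.5.2:** model the log response relative to the same-dose baseline, so that the curve uses the same kind of response as the primary endpoint. Summarise baseline and infusion values in the same way and from a stated number of readings; 11.2.1 gives a count only for infusions ("This cycle will be repeated approximately 8 times during the last 2 min of each infusion"). Add a version corrected for the concurrent non-infused arm, by log ratio or covariate.
2. **17.5.1 and 17.5.3:** keep the infused-arm percent change. Beside it, tabulate the percent change in the infused/non-infused ratio and each arm's raw FBF.
3. **8.1 and 11.2.1:** add one line confirming that both arms are measured at each baseline.

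Cost: wording and extra tables. Cuffs are already on both forearms and infusion readings are simultaneous, so no session time is added if both arms are read at baseline, as the procedure suggests. The primary endpoint is not redefined. The protocol text change would be documented as an amendment under 14.6, and the detail belongs in the SAP before database lock. The statistical price is some added noise when arm-specific variation dominates, or when a baseline is only weakly correlated with its own infusion. The raw infused-arm table lets a reader see that.

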11.3.2 Vital signs

Systolic and diastolic blood pressure and pulse will be measured in supine position after 10 min of rest at time-points specified in Table 8.1-1.

Any vital signs outside the normal ranges will be judged as not clinically significant or clinically significant by the Investigator. The assessment will be recorded in the eCRF. Abnormal post-dose values judged as clinically significant will be reported as AEs.

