17.1 General

Continuous data will be presented in terms of evaluable and missing observations, arithmetic mean, standard deviation (SD), median, minimum, and maximum value. Categorical data will be presented as counts and percentages. When applicable, summary data will be presented by treatment (test product/comparator), and by assessment time. Individual subject data will be listed by subject number, treatment, and, where applicable, by assessment time.

All descriptive summaries and statistical analyses will be performed using SAS Version 9.4 or later (SAS Institute, Inc., Cary, NC).

Baseline for the safety assessments will be defined as the last data collection point prior to the first administration of IMP. For the FBF measurements, a baseline will be defined for each dose level.

No imputation of missing data will be performed.

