17.6.2 Vital signs

Vital signs (systolic/diastolic blood pressure and pulse) will be summarised using descriptive statistics. Data will be presented with absolute change from baseline.

Individual data will be listed by subject.

17.6.3 12-lead ECG

All ECGs will be categorised as *normal, abnormal, not clinically significant*, or *abnormal, clinically significant* (as judged by the Investigator) and summarised using descriptive statistics.

Individual data will be listed by subject.

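### In subjects who complete all infusions, the only scheduled post-dose blood pressure and pulse reading follows both C21 and nitroprusside; one reading in the existing 20-min rest would follow C21 alone

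*Combined protocol and SAP*

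**What the plan says.** **Timing.** Table 8.1-1, footnote 3, places the Day 1 laboratory, vital signs and ECG assessments "Before first IMP administration and before leaving the clinic". The text of section 8.1 and the synopsis say the same. Section 11.3.2 adds no time point: blood pressure and pulse "will be measured in supine position after 10 min of rest at time-points specified in Table 8.1-1". The end-of-study contact is a phone call, so no later reading exists.

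**Sequence.** After cannulation, "a resting period of approximately 25 min will follow". Five ascending C21 infusions are then given, and "When the last C21 dose has been administered there will be a resting period of 20 min". Three nitroprusside infusions follow. The only measurement scheduled in that rest is the forearm blood flow (FBF) baseline at its end.

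**Objective and endpoint.** Section 7.2 states the safety objective as "To evaluate safety and tolerability of i.a. administrations of C21 to healthy male subjects". The related endpoint in section 7.2.1 is "Clinically significant changes in vital signs, ECG and safety laboratory parameters".

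**Analysis.** Section 17.1 sets a single reference value: "Baseline for the safety assessments will be defined as the last data collection point prior to the first administration of IMP". For vital signs, section 17.6.2 adds: "Data will be presented with absolute change from baseline". Section 17.1 also foresees summaries split by test product and comparator where applicable.

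**The concern.** The objective concerns C21, but in a completer the planned change runs from before any study drug to after both drugs. The second drug is a positive control that section 8.2.1 chose for its strong vasodilating action. The scheduled data therefore hold no blood pressure or pulse value that follows C21 and precedes nitroprusside, and the split by product foreseen in section 17.1 cannot be made for vital signs.

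Two consequences follow.

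- Section 11.3.2 turns clinically significant post-dose abnormalities into adverse events, and section 11.3.1.8 requires causality to be judged separately for C21 and Nipruss. For an abnormal discharge value without symptoms, no scheduled intermediate value supports that judgement.
- Section 8.2 argues that local infusion can keep drug-induced blood pressure changes small. No scheduled reading lets the study describe this after C21 alone.

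The primary FBF analysis is not affected.

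**Working it through.** **Check on the plan's own figure.** From Table 10.5-1, total C21 = 15 + 50 + 150 + 500 + 1,000 = 1,715 µg. This matches the 1.715 mg in sections 6.6 and 6.6.2. From Table 10.5-2, total nitroprusside = 4 + 8 + 16 = 28 µg.

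**Inputs for the timeline** (sections 8.1, 10.5 and 11.2.1): infusions of 5 min, wash-outs of at least 15 min between doses of either product, and a 20-min rest between products. Minute 0 is the start of the first C21 infusion.

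- End of last C21 infusion: 5 × 5 + 4 × 15 = 85 min
- Start of nitroprusside: 85 + 20 = 105 min
- End of last nitroprusside infusion: 105 + 3 × 5 + 2 × 15 = 150 min
- Minimum gap from the end of C21 to the discharge reading: 150 − 85 = 65 min
- If the 15-min wash-out drawn after the 200 µg/min dose in synopsis Figure 1 is additional to the 20-min rest: 65 + 15 = 80 min

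**What each reading follows in a completer.**

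| Reading | Earliest minute | C21 infusions before it | Nitroprusside infusions before it |
|---|---|---|---|
| Pre-dose (planned) | before 0 | 0 | 0 |
| 10 min into the rest (proposed) | 95 | 5 | 0 |
| Before leaving the clinic (planned) | 150 | 5 | 3 |

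Scheduled values after C21 and before nitroprusside rise from 0 to 1 per completer.

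**Does the reading fit in the rest?** By the end of the last C21 infusion the subject has been lying down for about 25 + 85 = 110 min. That alone does not clearly satisfy the 10-min rest condition. Section 11.2.1 places about 8 cuff cycles of roughly 7 + 8 = 15 seconds in the last 2 min of each infusion, with the wrist cuffs above systolic pressure. A reading about 10 min after those cycles end meets the condition on either interpretation.

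The time then left before wrist-cuff inflation is 20 − 10 − 0.5 − L. Here 0.5 min is the 30 seconds in section 11.2.1, and L is the length of the FBF baseline. The protocol does not state L; I assume 2 to 5 min, inside the 20-min rest:

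- L = 2: 7.5 min
- L = 5: 4.5 min

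The reading must be taken, and the arm repositioned if it was moved, within that margin.

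**The case against.** **The plan is consistent with itself.** The synopsis and sections 8.1, 11.3.2, 17.1 and 17.6.2 agree. A before-and-after check is a coherent choice for an endpoint of clinically significant changes judged by the investigator. This stands: the point is about a design choice, not a contradiction.

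**Little is expected.** Total C21 is 1.715 mg, against a single oral dose of 200 mg that section 6.6.2 describes as established and safe. Section 6.3 reports 134 exposed subjects. Sections 6.4 and 6.6 describe local doses as 10 to 100 times below those with systemic effects. The newer risk is local tolerance, which a cuff reading does not address. This also stands and is why the gain is only modest.

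**Other cover exists.** The investigator interviews the subject about adverse events between doses (8.1), staff-observed events are recorded (11.3.1.11), causality is judged per product (11.3.1.8), and section 8.2 promises careful monitoring of well-being. A reader might infer that blood pressure goes unwatched between infusions. The documents do not support that, since unscheduled readings are not ruled out. But an interview would not detect a symptomless change, and section 8.2 names no measurement.

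**The new value would not isolate C21.** A reader might infer that it would measure the C21 effect on blood pressure. It would not. There is no placebo, the order is fixed, and footnote 3 does not place the pre-dose reading relative to cannulation, the meal or the rest. The change may include all of these, together with 85 min of infusions and cuff cycles. It separates C21 from nitroprusside and from nothing else.

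**The reading could intrude on FBF.** One arm holds the arterial catheter. The other is the control arm, with cuffs and strain-gauge, held above heart level (11.2.1). A cuff inflation or arm movement could disturb it before the nitroprusside baseline. This is a real cost, and it governs where in the rest the reading is placed.

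**Conclusion.** The point holds as an optional, low-cost improvement. For subjects who receive all eight infusions, the only scheduled post-dose blood pressure and pulse value comes after both products, at least 65 min (or 80 min) after C21 ends. The change in section 17.6.2 cannot be attributed to one product or the other. A subject stopped before nitroprusside would already give a value after C21 only.

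Three limits apply.

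- The 65 and 80 min are minimums. The synopsis plans about 4 hours (240 min), while the minimum sequence is 25 + 150 = 175 min. A reader might place all the spare time after C21 and infer a much longer gap, but the documents do not say where it falls.
- The size of any blood pressure effect cannot be estimated from the documents, which expect it to be small. Nothing here shows that an effect is being missed.
- The added value would be descriptive, in five subjects, after all five C21 doses together, and confounded with time and procedure. ECG and laboratory changes share the same two time points and would stay combined.

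**What to change.** **Schedule (Table 8.1-1 and section 11.3.2).** Add one supine blood pressure and pulse reading in the first half of the existing 20-min rest, before any nitroprusside. State how the 10-min rest condition is met, for example by reading about 10 min after the last C21 infusion and its FBF cuff cycles end. Complete it well before the wrist-cuff inflation and FBF baseline at the end of the rest.

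**Comparability.** Specify the arm and arm position, which section 11.3.2 leaves open, and use the same ones for the Day 1 pre-dose reading. State when that pre-dose reading is taken relative to cannulation and rest.

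**Analysis (section 17.6.2, or the separate analysis plan announced in section 17).** Report the new value as *change after C21, before nitroprusside*, not as a C21 effect. Label the discharge change as following both products, and say that ECG and laboratory changes remain combined. The discharge label is worth adding even if the extra reading is declined.

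**Cost.** A schedule amendment, a few eCRF fields, one cuff inflation and a little staff time. The main downside is possible brief disturbance of the instrumented control arm before the nitroprusside FBF baseline; an arm moved for the reading must be back in position before then. The change concerns measurement only; no dose or clinical rule is proposed.
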